3.4. DATA COLLECTION AND INSTRUMENTS

A sample of patients with a distal radius fracture operated in our Hospital will be obtained. Those who meet the inclusion criteria will be asked to participate and will be told what the study is about. Those who accept must sign the specific informed consent of this study.

Prior to surgery, an external observer will collect the personal data of the patients, assign them a code (P1, P2, P3...) and perform the anamnesis following the Data Collection Guide Form

Patients' recruitment will be done during a year, from December 2020 to December 2021. They will be separated into two groups. The external observer will do this process with 10-block randomization using Study Randomizer (2017), a web based randomization service (19)

The first (Group A) in which WALANT technique will be performed and the second (Group B) in which locoregional anaesthesia (either axillary or supraclavicular block) with axillary ischemia will be applied. Because it is considered a long-term intervention, all patients will be offered the option of sedation or not, and this variable may change depending on the criteria of anaesthesia or the patient himself in order to facilitate their well-being. All patients participating in the study will receive the same antibiotic prophylaxis following our protocol (Cefazolin 1g iv in <80Kg or 2g 80-160Kg and in patients with normal renal function, to pass in 5 minutes. In those with FG The dose should be adjusted, and a second dose of 2g iv should be given if the surgery lasts 3 hours or more. In patients with penicillin allergy, Teicoplanin 600mg iv will be administered in 10 minutes, without repeating the dose. in no case) (20)

Group A (WALANT Anaesthesia +/- sedation + NO ischemia)

In WALANT technique, the doses are followed according to Lalonde's (21). 1% lidocaine with 1: 100,000 adrenaline is generally used to counteract the acidic pH of lidocaine, which is buffered with 8.4% (1M) sodium bicarbonate in a 10: 1 ratio to decrease pain during administration. If more volume is required, Lidocaine is diluted to 0.5% so as not to exceed the maximum toxic dose of 7mg / kg with a maximum total dose of 500mg (50ml of 1% Lidocaine or 10cc of 5% Lidocaine) (22)

In this case, the preparation will be made by the nurse with 100cc of SF, from which 15cc will be extracted and 10cc of 5% Lidocaine + 1cc Adrenaline + 4cc of 1M Bicarbonate will be added.

Anaesthesia will be administered in the operating room, monitoring the patient's HR, BP, and SatO2. It will take 20-30 minutes before starting the surgery, as the peak of vasoconstrictor action of the adrenaline is reached after this time.

The technique according to Ahmad (10) is to infiltrate 40ml of local anaesthetic preparation, distributing 10ml to the subcutaneous tissue along the approach, from proximal to distal. Subsequently, 30ml is administered in deeper planes divided into

3 points, from proximal to distal, distributed in 4ml around the flying periosteum, 2ml radially and 4ml in the dorsal periosteum, through a lateral entrance, introducing the 'needle from the radial side avoiding puncturing through the radial artery. An additional 10ml will be added for the intra-articular region, using conventional 3-4 and 6R arthroscopy radiocarpal approaches. In some cases it may be increased if the surgeon considers that it requires more volume, as long as we do not exceed the toxic doses (23).

In patients with a history of cardiac pathology, it is possible to assess the possible dissolution of adrenaline at 1: 400000, this group will include those patients with ischemic heart disease and / or severe hypertension (irregular hypertension with the use of 3 different antihypertensive drugs).

Group B (Locoregional anaesthesia proximal block +/- sedation + ischemia)

The anaesthesiologist in charge of the operating room will perform the locoregional block. The same ischemia sleeve (size, brand, manufacturer and country of origin) will be used on all patients and the same ischemia pressure (250mmHg) will be applied.

In all of them, intraoperative monitoring will be performed, which will be the same in both groups, the FC, FR, TA, ECG, SatO2 and duration of the intervention must be recorded.

The surgical procedure will be the same for all patients. If the surgeon considers it necessary, arthroscopic assistance will be used with conventional dorsal radiocarpal portals (2-4R and 6R). Surgeons from the surgeons of our Upper Extremity Unit will perform all operations.

As for the postoperative period, the participants in both groups will require 24-48 hours of admission and will perform the first treatment on the floor before hospital discharge. They will receive a sheet with the guideline of rehabilitation exercises to be performed at home, with plaster and without (Appendix 5) so we make sure that everyone receives the same instructions to avoid swelling and promote mobility.

A first check-up will be performed at 10-15 days for treatment and a second check-up will be performed one month after the operation.

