2.1. PRIMARY OUTCOMES

1. Pain (Difference between preoperative and postoperative EVA (24 hours, 10-15 days after surgery, 1 month after surgery))
 - a. Analgesia intake
2. Swelling (difference with healthy limb and difference between preoperative and postoperative (24 hours, 10-15 days after surgery, 1 month after surgery))
3. Patient satisfaction (Scale 1-5 and questionnaire)

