3.3. VARIABLES

Independent variables:

These variables will be collected during the surgery and in the subsequent from patient anamnesis, clinic history and filling the Collection Data Guide Form:

- Age (years)
- Sex (male / female)
- Dominant hand (left / right / both)
- Injured hand (left / right / two)
- Fracture classification according to American Orthopaedic (AO) (16), (17)
- Number of days from injury to surgery (days)
- Preoperative pain (VAS scale (18))
- Preoperative swelling injured hand and healthy hand. The perimeter of the wrist will be measured at the height of the proximal palmar fold in cm.

Dependent variables:

These variables are the ones we want to study and will be collected during the surgery and afterwards from patient anamnesis, clinic history and filling the Collection Data Guide Form:

- Duration of admission (hours).
- Duration of surgery (minutes).
- Duration of ischemia in group B (minutes).

- Preoperative and postoperative pain (VAS scale): Pain at baseline, 24 hours post-intervention, at the visit of the first treatment 10-15 days post-intervention and pain 1 month after the intervention.
- Intraoperative pain (VAS scale): Assessable only if it has not required sedation.
- Time (minutes) of anaesthesia administration
- Time (minutes) from the end of administration to the beginning of IQ
- Need for anaesthetic reinforcement:
 - Sedations (yes/no) and reason
 - In the case of WALANT: Taking into account the reference technique used (10), if any extra doses are needed and location within the wrist
- Postoperative analgesia during admission and discharge (drugs used, dose and frequency of use)
- Postoperative swelling injured hand and healthy hand (cm).
- Stained dressing and the presence of active bleeding due to the wound within 24 hours and during the first outpatient clinic 10 or 15 days after surgery.
- Patient satisfaction during the first outpatient clinic 10 or 15 days after surgery. → Assess satisfaction (1-5) / Would you repeat the anaesthesia type? / Would you recommend the technique?
- Description of the complications of anaesthesia.
- Description of postoperative complications.
- Mobility 24 hours post-intervention, first aid and one month later. (The mobility of the fingers, intrinsic and extrinsic muscles, Kapandji exercises 1-10 and wrist mobility will be assessed by measuring flexion-extension and prone-supination with a goniometer).
- Surgeon's experience

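### The plan names nobody to read swelling and mobility unaware of the arm, and the external observer who takes the baseline data also runs the randomisation

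*Combined protocol and SAP*

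**What the plan says.** Section 3.4 gives the external observer two tasks. The first is the pre-surgery record: "Prior to surgery, an external observer will collect the personal data of the patients, assign them a code", together with the history on the Data Collection Guide Form. The second is allocation: "The external observer will do this process with 10-block randomization using Study Randomizer (2017), a web based randomization service".

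Section 2.1 lists as a primary outcome "Swelling (difference with healthy limb and difference between preoperative and postoperative (24 hours, 10-15 days after surgery, 1 month after surgery". Section 3.3 gives the method: "The perimeter of the wrist will be measured at the height of the proximal palmar fold in cm". Mobility is a secondary outcome in section 2.2. Section 3.3 times it as "Mobility 24 hours post-intervention, first aid and one month later" (the middle time appears to be the 10-15 day check-up) and has wrist motion read with a goniometer. Neither section names the person who takes these readings.

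On the operation itself, section 3.4 says "The surgical procedure will be the same for all patients". Section 3.4 also gives both groups the same admission, exercise sheet and check-ups.

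**The concern.** A tape perimeter and a goniometer angle both depend on where the reader places the instrument and how the scale is read. The hypothesis at the end of the Introduction is directional: it expects less swelling and pain with the local technique. A reader who knows the arm and the hypothesis may lean slightly one way without intending to. Such a lean looks the same as a treatment effect, and the group comparisons in section 3.6 can neither detect nor correct it.

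At stake is one of the three primary outcomes in section 2.1, and the one for which blinded reading is most feasible, because pain and satisfaction come from the patient. The present division of tasks gives the allocation to the person described as external, who could otherwise have stayed unaware of it.

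**Working it through.** **Step 1. Who knows the arm, from the roles named in section 3.4**

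| Role | What the plan has them do | Knows the arm? |
|---|---|---|
| External observer | Pre-surgery data, coding, randomisation | Yes, by running the allocation |
| Surgeon | Operates with or without the cuff | Yes, through care |
| Anaesthesiologist | Performs the block in group B | Yes, through care |
| Nurse | Makes the group A preparation | Yes, through care |
| Person reading perimeter and mobility after surgery | Not named | Not stated |

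**Step 2. Is masking covered elsewhere?** Section 3.3 says only that the dependent variables come from history-taking, clinical records and the form. Section 3.8 uses dissociated tables to protect participants' data. That is confidentiality, and it does not say that the arm is hidden from whoever measures. The limitations section mentions the subjectivity of the VAS but not the absence of blinding, so nothing shows that open assessment was a considered choice.

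**Step 3. Could these outcomes be read without the arm?** Yes. Neither reading needs it, and the operation and follow-up schedule are common to both groups. Allocation is web-based, so someone other than the observer can open it.

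**Step 4. Illustration of size.** The plan gives no sample size, SD, effect size or power, so there is no figure of its own to reproduce.

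- From the plan: 5% significance level (section 3.6). It does not state sidedness; two-sided is assumed.
- Assumed: *n* = 20 to 100 per arm; a systematic between-arm reading shift of *b* SD; no true effect; normal approximation.

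The shift moves the test statistic by δ = *b*√(*n*/2). The rejection probability is Φ(δ − 1.96) + Φ(−δ − 1.96).

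- *n* = 20, *b* = 0.2: δ = 0.2 × √10 = 0.632; Φ(−1.328) + Φ(−2.592) = 0.092 + 0.005 = 0.097.
- *n* = 100, *b* = 0.2: δ = 0.2 × √50 = 1.414; Φ(−0.546) + Φ(−3.374) = 0.293 + 0.000 = 0.293.

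| *n* per arm | *b* = 0 | *b* = 0.1 | *b* = 0.2 | *b* = 0.3 |
|---|---|---|---|---|
| 20 | 5.0% | 6.2% | 9.7% | 15.8% |
| 30 | 5.0% | 6.7% | 12.1% | 21.3% |
| 50 | 5.0% | 7.9% | 17.0% | 32.3% |
| 100 | 5.0% | 10.9% | 29.3% | 56.4% |

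For a fixed shift the error rate rises with *n*, so recruiting more patients does not cure the problem.

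**The case against.** A reader might infer that every assessor will know the arm. The documents do not say so. They describe the observer's data role only before surgery and leave the postoperative reader unnamed. Ward or clinic staff might take the readings, and what they know is not stated. A reader might also infer that the observer is the trial's one independent person, but the text says only external. Both objections stand. The gap is that no blinded reader is specified, not that an unblinded one is.

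The Data Collection Guide Form is not in the supplied text, so it may name an assessor. That stands as a caveat. If it does, section 3.4 should say so.

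Blinding would leak. The section 3.3 variables include ischemia time in group B, extra doses in group A, and satisfaction questions about the anaesthesia at 10-15 days, before the 1-month reading. Infiltration around the wrist or a cuff may leave marks. This stands, and it shapes the fix: simply reassigning the allocation would not be enough. Partial blinding still limits the bias.

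Using people already in the trial is an inference. The plan does not show that the observer is free at three postoperative readings. This stands as a cost.

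Moving the allocation to treating staff might weaken concealment, since blocks of 10 allow some anticipation of later assignments. This has little force if those staff do not enrol patients and the allocation is opened only after enrolment and baseline are saved.

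Finally, nothing in the documents supports any particular bias. That stands: the percentages are not estimates for this trial.

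**Conclusion.** The concern holds in this form: as written, the plan lets swelling and mobility be read by someone who knows the arm, every named role does know it, and nothing requires otherwise. How far this would distort the results cannot be determined from the documents. Under the stated assumptions (no true effect, two-sided 5% test, 20 to 100 per arm), a shift of 0.1 SD gives a false-positive rate of 6.2% to 10.9%, and 0.2 SD gives 9.7% to 29.3%. Both the shift and the sample size are assumed.

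The reach is limited to swelling among the primary outcomes and mobility among the secondary ones. The change should be made, because it is cheap and the bias cannot be removed at analysis.

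**What to change.** Amend section 3.4 as follows.

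1. The observer saves baseline VAS and both wrist perimeters before allocation is opened.
2. The web allocation is then opened by operating-room staff who must learn the arm anyway and who do not enrol patients.
3. Perimeter and goniometer readings at 24 hours, 10-15 days and 1 month are taken by the observer, or by ward or clinic staff already seeing the patient. Whoever reads is not told the arm.
4. Arm-revealing items (ischemia time, anaesthetic reinforcement, satisfaction with the anaesthesia) go on a separate sheet, completed by someone else at the times already planned.
5. Patients are asked not to mention their anaesthesia to the reader, and any unmasking is recorded.

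Add to the limitations that patients and treating staff know the arm, so pain and satisfaction remain open to that influence.

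The cost is a few sentences of text, a split form and a reassignment of tasks. No treatment or visit changes. The reader must be available at the existing follow-up times, which may be a new duty for the observer. Blinding will be incomplete, most of all at 24 hours.

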Is WALANT Applicable in Distal Radius Fracture Osteosynthesis?

Study Protocol and Statistical Analysis Plan

October 2020

NCT (still not available)

ABSTRACT

Title → Is WALANT Applicable in Distal Radius Fracture Osteosynthesis?

Aims → To evaluate is Wide Awake Local Anaesthesia No Tourniquet (WALANT) is applicable to distal radius fracture (DRF) osteosynthesis and possible benefits of not using the ischemia cuff in distal radius osteosynthesis, by using the WALANT anaesthetic technique and compare it with patients who have undergone the current anaesthesia method (locoregional anaesthesia with or without sedation)

Material and methods → Randomized controlled study comparing patients operated on for distal radius fracture with osteosynthesis during a year (December 2020 to December 2021). The randomization will be done by 10 block in order to ensure similar numbers of patients in both groups of intervention. In the group A patients will be operated on with local anaesthesia (lidocaïne + adrenaline + bicarbonate) with or without sedation without the use of ischemia, while in group B patients will be given anaesthesia by proximal locoregional blockade with or without sedation and ischemia cuff. Immediate short-term results will be compared between both groups. Primary outcomes will be preoperative and postoperative pain, pre and postoperative swelling, and patient and surgeon satisfaction.

Results →

Conclusion →

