3. MATERIAL AND METHODS

3.1. TYPE OF STUDY

This is a randomized prospective study comparing two groups of patients with distal radius fracture during a year

A → Local Anaesthesia (WA) LANT + NO ISCHEMIA +/- sedation.

B → Locoregional anaesthesia proximal block + ISCHEMIA +/- sedation.

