3.7. PLACE AND TIME OF STUDY

The centre where the study will be carried out is the Arnau University Hospital of Vilanova de Lleida (HUV), belonging to the Catalan Institute of Health, is the reference centre for acute patients in the health regions of Lleida and the High Pyrenees and Aran.

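### Fixed blocks of 10 in one hospital with visibly different arms: up to about 17% of allocations could be known in advance, and the protocol does not lock baseline data before allocation

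*Combined protocol and SAP*

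**What the plan says.** The Abstract (Material and methods) gives the scheme and its purpose: "The randomization will be done by 10 block in order to ensure similar numbers of patients in both groups of intervention". Section 3.4 repeats it and names the person and the tool, a web service: "The external observer will do this process with 10-block randomization using Study Randomizer (2017". The same person does the intake: "Prior to surgery, an external observer will collect the personal data of the patients, assign them a code", followed by the history.

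Section 3.7 names one hospital, and Section 3.4 says that surgeons of one unit do all the operations. The arms in Section 3.1 differ visibly in theatre: group A is "Local Anaesthesia (WA) LANT + NO ISCHEMIA +/- sedation", and group B has a proximal block and a cuff.

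The documents do not mention varying block sizes, stratification, an allocation ratio, masking of anyone, or a concealment procedure. The dissociated tables in Section 3.8 protect confidentiality; they do not mask allocation.

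On timing, Section 3.4 puts the history before surgery. Section 3.3 says that the independent variables, which include preoperative pain and swelling, are collected during surgery and afterwards.

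**The concern.** In a permuted block of known size, once one arm has used its places the rest of the block is determined. A web service hides the list, but it does not hide the running balance from a person who sees each allocation as it is issued.

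Knowing or strongly suspecting the next arm could affect who is approached, when surgery is listed, or whether a judgement-based exclusion is applied. Section 3.2 has several of these, such as a seriously injured limb or poor skin condition. Section 3.5 says that more complex fractures can cause more pain and that the sample may be small. Section 3.6 plans only unadjusted two-group tests, so a difference in case mix created at enrolment would pass straight into the pain and swelling comparisons.

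A related gap concerns baseline values. Pain and swelling are primary outcomes defined partly as change from the preoperative value (Section 2.1). If that value may be recorded after the arm is known, half of the change score is exposed to knowledge of allocation.

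**Working it through.** The plan gives no sample size and no predictability figure, so there is nothing of its own to reproduce.

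**Inputs**
- Block size 10 (Abstract, Section 3.4). I read the phrase as blocks of ten patients; it could also mean ten blocks.
- Two arms (Section 3.1).
- Ratio 1:1, that is 5 + 5 per block. This is inferred from the aim of similar numbers.
- One sequence: one hospital (Section 3.7) and no stratification.

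**1. Certain allocations, fixed block of 2m = 10**
- Expected number per block = 2m/(m + 1) = 10/6 = 1.67.
- Share = 1/(m + 1) = 1/6 = 16.7%.
- Enumerating all C(10,5) = 252 blocks gives the same value. The last place is always certain, and 44.4% of blocks have two or more certain places.
- For assumed totals of 40, 60 and 100 patients, 1/6 is about 6.7, 10 and 16.7 allocations.

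**2. Best-guess success when following the balance**
- [m + 2^(2m−1)/C(2m,m) − 0.5]/(2m) = [5 + 512/252 − 0.5]/10 = 6.53/10 = 65.3%, against 50% by chance.
- The share predictable with at least 80% certainty is 19%.

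**3. Incomplete knowledge**

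The 16.7% needs the block size, the block starts and every earlier allocation. If each earlier allocation is seen independently with a given probability (block starts still known), simulation gives:

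| Probability that an earlier allocation is seen | Certain allocations |
|---|---|
| 1 | 16.7% |
| 0.9 | 9.8% |
| 0.75 | 3.9% |
| 0.5 | 0.5% |

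If only group A cases can be recognised, certainty arises only when group A is used up first. By symmetry that is half the total: 16.7%/2 = 8.3%.

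**4. Effect of varying the block size**

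Simulation (1,500 sequences each of 60 and 100 patients). The observer knows the possible sizes and all earlier allocations, and updates by Bayes' rule.

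| Scheme | Certain | Predictable at 80% or more | Best-guess success |
|---|---|---|---|
| Fixed 10 | 16.7% | 19% | 65% |
| Random 8, 10, 12, 14 | about 0.7% | about 8% | about 64% |

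**5. Price in balance**

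The worst imbalance when recruitment stops is half the largest block: 10/2 = 5 now, and 14/2 = 7 with sizes up to 14.

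**The case against.** A reader might infer that the design simply makes 17% of allocations certain, and that anyone who counts cuffs in theatre knows the end of each block. The documents do not support that. The Abstract calls locoregional anaesthesia the current method, and group B combines it with a cuff. Patients outside the trial may well be operated on in the same way, so a cuff does not reliably mark a group B allocation. Theatre staff also see the order of surgery, which need not be the order of randomisation, because the interval from injury to surgery varies (Section 3.3).

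The external observer could follow the sequence exactly. The documents do not say, however, that this person judges eligibility, approaches patients or lists surgery. Section 3.4 also describes eligibility, consent, history and randomisation in a sensible order, although it does not make that order binding.

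Ten is already a fairly large block: fixed blocks of 4, 6 and 8 give 33.3%, 25% and 20% certain allocations. Varying the size hardly changes overall guessing success. Nor does it cure exclusion 6 in Section 3.2 (a different surgical technique was required), which can be applied after the arm is known under any block scheme.

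All of this stands. It limits the size of the concern and makes the order of steps at least as important as the block size. It does not remove the concern: one fixed size is written in the protocol, one person sees every allocation, and nothing locks the data before the arm is released.

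**Conclusion.** The point holds as an inexpensive improvement to a defensible scheme. It is not an error that invalidates the trial. At most 16.7% of allocations could be known in advance, by someone with complete knowledge of the sequence such as the external observer. With partial knowledge the figure is about 10%, 4% or less.

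This rests on reading the block phrase as a fixed size of 10, on an inferred 1:1 ratio, and on the absence of any masking text; the documents never call the trial open. If ten blocks were meant, their size is undefined and the sentence still needs correcting.

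A reader might go further and conclude that enrolment will be steered. The documents show only that it could be. Varying block sizes would remove near-certainty but not predictability in general, so the rule on the order of steps is an essential part of the remedy.

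**What to change.** - **Abstract and Section 3.4:** replace the block phrase with 1:1 permuted blocks of randomly varying size, set in the same web service. State that the sizes are withheld from the protocol and from every document held by recruiting or operating staff. The set 8, 10, 12, 14 above is only an illustration; the sizes chosen should not appear in the protocol text.
- **Section 3.4:** require signed consent, confirmed eligibility, baseline VAS and the baseline perimeters of both wrists to be saved before the allocation is requested.
- **Section 3.3:** correct the timing statement so that preoperative pain and swelling are recorded before allocation, consistent with Section 3.4.

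The cost is a settings change, a few sentences of text, and a worst-case final imbalance of 7 patients instead of 5 if sizes go up to 14. If recruitment has begun, the rule on order can still be adopted, and the report should state the block size used and who knew it.

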The most commonly used drug for local anaesthesia is lidocaine, as it is the prototype short-acting anaesthetic and its physicochemical properties (solubility, relative potency, onset of action and duration) are those indicated to perform this type of procedure. The injection of lidocaine may or may not be associated with adrenaline, which produces vasoconstriction, decreasing local bleeding in the area, and at the same time prolongs the action of lidocaine. This combination of drugs can extend the duration of anaesthesia up to 3 hours. That is why in the WALANT technique these two drugs are administered together. Lidocaine is administered with a 1% (10mg / ml) solution, and if larger volumes or lower doses of anaesthesia are required, 0.5 of the solution may be used to avoid the maximum toxic doses, which in the combination of adrenaline + lidocaine, the maximum toxic dose is 7mg / kg with a maximum total dose of 500mg (50ml of 1% Lidocaine or 10cc of 5% Lidocaine). Concentrations above 1% lidocaine are not used, as they have not been shown to improve induction or duration of anaesthesia and may increase the risk of toxicity. In order to counteract the acidic pH of lidocaine, it is buffered with 8.4% (1M) sodium bicarbonate in a 10: 1 ratio, thus reducing pain during administration. This type of anaesthesia is performed according to the Lalonde's technique and is administered according to the Ahmad technique. (10) (22) (23) (24)

Our hypothesis is that the application of this anaesthetic technique, combined or not with sedation, causes less swelling and pain in the immediate postoperative period, without compromising patient satisfaction, altering short-term results or increasing the number of complications and without increasing the technical difficulty of the procedure to the surgeon.

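### The group A recipe does not give the stated 10:1 bicarbonate ratio, leaves the study lidocaine strength ambiguous, and makes a 0.5% solution for which the lidocaine ceiling has no ml figure

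*Combined protocol and SAP*

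**What the plan says.** The description and the recipe are in section 3.4 under Group A. Part of the description also appears in the Introduction.

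- **Strength as described.** The Introduction says "Lidocaine is administered with a 1% (10mg / ml) solution" and allows a 0.5 dilution when larger volumes or lower doses are needed. Section 3.4 says "1% lidocaine with 1: 100,000 adrenaline is generally used", and then "If more volume is required, Lidocaine is diluted to 0.5" (per cent), so that the toxic dose is not exceeded.
- **Buffer as described.** Section 3.4 says the solution is "buffered with 8.4% (1M) sodium bicarbonate in a 10: 1 ratio to decrease pain during administration". The Introduction gives the same ratio.
- **Ceiling.** Both places give 7 mg/kg with a "maximum total dose of 500mg (50ml of 1% Lidocaine or 10cc of 5% Lidocaine").
- **Recipe.** The nurse starts with a 100cc bag of SF. The instruction is then: "15cc will be extracted and 10cc of 5% Lidocaine + 1cc Adrenaline + 4cc of 1M Bicarbonate will be added". No other recipe is given.
- **Volume.** The plan is 40 ml of infiltration plus 10 ml into the joint. Beyond that, "it may be increased if the surgeon considers that it requires more volume, as long as we do not exceed the toxic doses".
- **Adrenaline.** A 1:400,000 dilution may be considered in cardiac patients. It has no recipe, and the stock strength of the 1cc in the recipe is not stated.
- **Recorded data.** Section 3.3 lists whether extra WALANT doses were needed and where in the wrist. It lists neither body weight nor total ml injected.

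**The concern.** This solution defines the experimental arm, so a reader should be able to recover one composition from the protocol. Instead, the descriptive text and the recipe disagree on the buffer and leave the lidocaine strength open. The safety ceiling is not expressed in the units the surgeon injects.

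Three things are at stake:

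- **Interpretation.** Intraoperative pain, anaesthetic reinforcement and insufficient anaesthesia are all collected, and all depend on what was injected. The protocol itself links the buffer to pain on injection.
- **Safety.** The rule for added volume relies on a ceiling that staff must convert themselves for a 0.5% bag.
- **Verification.** With neither weight nor total volume among the listed variables, adherence to the 7 mg/kg limit could not be checked from the trial data.

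**Working it through.** **Inputs.** All are from section 3.4: 100 ml bag; 15 ml removed; 10 ml of 5% lidocaine (50 mg/ml), 1 ml adrenaline and 4 ml of 1M bicarbonate added; ceiling 7 mg/kg, maximum 500 mg; planned volume 40 ml plus 10 ml. I take the bag to hold exactly 100 ml at the start.

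**1. The plan's own ml figures for the ceiling.** 50 ml × 10 mg/ml = 500 mg, and 10 ml × 50 mg/ml = 500 mg. Both are correct and agree with each other.

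**2. What the recipe makes.** Volume: 100 − 15 + 10 + 1 + 4 = 100 ml. Lidocaine: 10 × 50 = 500 mg. Concentration: 500 / 100 = 5 mg/ml = 0.5%. This is half the strength described as usual and equal to the larger-volume strength.

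**3. Bicarbonate ratio.** The stated value is 10:1.

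| Compared with 4 ml bicarbonate | Ratio |
|---|---|
| 10 ml lidocaine stock | 10/4 = 2.5:1 |
| Stock plus adrenaline, 11 ml | 11/4 = 2.75:1 |
| 1% equivalent of 500 mg, 50 ml | 50/4 = 12.5:1 |
| Rest of the bag, 96 ml | 96/4 = 24:1 |
| Finished bag, 100 ml | 100/4 = 25:1 |

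Dividing the 40 ml infiltrated by 4 ml appears to give 10:1, but 40 ml drawn from the bag carries only 40 × 4/100 = 1.6 ml of bicarbonate, which is again 25:1.

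**4. Planned volume against the 7 mg/kg limit.** The injection steps add up: 10 + 3 × (4 + 2 + 4) = 40 ml, and 50 ml with the intra-articular part. The weight below which a dose exceeds 7 mg/kg is dose / 7.

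| Volume | At 0.5% | Exceeds below | At 1% | Exceeds below |
|---|---|---|---|---|
| 40 ml | 200 mg | 28.6 kg | 400 mg | 57.1 kg |
| 50 ml | 250 mg | 35.7 kg | 500 mg | 71.4 kg |
| Full 100 ml bag | 500 mg | 71.4 kg | not applicable | not applicable |

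After the planned 50 ml, another 50 ml remains in the bag. The whole bag is 500/50 = 10 mg/kg at 50 kg and 500/60 = 8.3 mg/kg at 60 kg.

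**5. The existing ceiling converted to ml.** The formula is min(500, 7 × weight) / concentration. At 5 mg/ml the weight limit is 7/5 = 1.4 ml/kg.

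| Weight | Ceiling | ml at 0.5% | ml at 1% |
|---|---|---|---|
| 50 kg | 350 mg | 70 | 35 |
| 60 kg | 420 mg | 84 | 42 |
| 70 kg | 490 mg | 98 | 49 |
| 80 kg | 500 mg | 100 | 50 |

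The protocol prints only the 50 ml figure for 1% and the 10cc figure for the 5% stock.

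**6. Adrenaline.** The stock strength is not given, so this step is an assumption over a range. In 100 ml, 1 ml of a 1 mg/ml stock gives the stated 1:100,000, a 0.5 mg/ml stock gives 1:200,000, and a 0.1 mg/ml stock gives 1:1,000,000.

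**The case against.** The best defence is that the recipe is simply the 0.5% option that section 3.4 already allows. Its opening phrase can be read as pointing back to that option. The stated reason for diluting is to stay under the toxic dose, and 50 ml at 1% would pass 7 mg/kg below 71.4 kg. On this reading the strength is not a contradiction, and I accept that. What remains is ambiguity. If the recipe is for the larger-volume case, the usual 1% solution has no recipe and no rule says who receives it. If the recipe is for everyone, the description of the usual solution is not the study solution.

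A reader might infer that the ceiling cannot be applied correctly. The documents do not support that. The ceiling is also given in mg/kg and mg, and the 10cc of 5% lidocaine it mentions is exactly what goes into the bag, so one bag equals the 500 mg maximum and 1.4 ml/kg follows in one step. Applying the printed 50 ml to this bag by mistake would stop at 250 mg, below the 500 mg maximum.

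A reader might also infer that centres would give doses differing twofold. Section 3.7 names one hospital, and a twofold difference needs someone to make up a 1% solution for which there is no recipe.

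On recording, weight is already needed for the weight-banded cefazolin dose, so it will be known at the bedside. The data collection form is not in the supplied text, so I can say only that section 3.3 does not list weight or total volume.

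The buffer mismatch survives all of this. It can be argued that 10:1 is stated alongside the 1% solution only, but even the 1% equivalent gives 12.5:1.

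**Conclusion.** The point holds in this form. The one recipe does not give the stated 10:1 buffer on any basis tried (2.5:1 to 25:1). It makes 0.5% lidocaine where the text gives 1% as usual, so the study strength is ambiguous rather than plainly contradicted. The ceiling lacks an ml figure for the solution the recipe makes.

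The planned volumes are not the problem. At 0.5% they stay within the protocol's own 7 mg/kg above 35.7 kg, in a trial of adults, so it would be wrong to conclude that the plan as prepared overdoses patients. The exposure lies in added volume: below 71.4 kg the weight limit is reached before the bag is empty. The protocol already forbids passing that limit but does not show it in ml.

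These results use only the document's figures and a bag of exactly 100 ml. The adrenaline dilution alone needs an outside assumption. The missing stock strength and the missing 1:400,000 recipe are omitted details, not arithmetic errors. I take no view on which strength, ratio or limit is right.

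**What to change.** 1. Reconcile the Introduction with the Group A text of section 3.4 in one preparation statement. It should give the final lidocaine concentration in mg/ml, the adrenaline stock strength and final dilution, and a bicarbonate ratio with its basis named, all agreeing with the recipe. If more than one strength or adrenaline dilution is intended, give a recipe for each and say who receives it.
2. Restate the protocol's existing ceiling as total ml by body weight for the solution actually prepared, covering planned plus added volume.
3. Add body weight and total ml injected to section 3.3 and, if they are not already there, to the data collection form.

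The choice of strength, ratio and limit belongs to the sponsor's clinicians. The cost is a paragraph of protocol wording, a short table and two data fields. No visit, procedure or sample size changes, and weight is already needed for antibiotic dosing.
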